### 5.2 CONTINUOUS OUTCOMES

The continuous secondary outcomes:

- Duration of symptoms rated ‘moderately bad’ or worse,
- Number of days of antibiotic use (total and split by penicillin and non-penicillin, and antibiotic class)
- Defined daily dose (DDD) (total and split by penicillin and non-penicillin and antibiotic class),
- And length of hospital stays,

will be analysed using a linear mixed effects regression model. The models will include randomised group, age, number of antibiotic prescriptions in the 24 months prior to randomisation (12 months for those recruited to the nested pilot study), and the number of QOF registered diseases as fixed effects. GP practice will be included as a random effect. The adjusted mean difference between the randomised groups with 95% confidence intervals and P-values will be reported.

The proposed analyses assumes that these secondary outcomes satisfy the assumptions of the linear mixed effects regression model. Histograms of the distribution of each outcome split by randomised group, and post estimate plots of the residuals will be presented. If the post estimate plots show evidence that the assumptions of the linear mixed effects regression model have been violated, transformation of the data will be attempted. If there is still evidence that the assumptions have been violated a quantile regression will be implemented. The quantile regression will include randomised group, age, number of antibiotic prescriptions in the 24 months prior to randomisation (12 months for those recruited to the nested pilot study), number of QOF registered diseases, and GP practice as covariates. The adjusted median difference between the randomised groups with

95% confidence intervals, and P-values will be reported. If the quantile regression does not converge an unadjusted quantile regression will be attempted; if the model still does not converge a non-parametric approach such as a Mann-Whitney U test will be adopted.

Defined daily dose (DDD) split by class, is expected to be small for some classes in each randomised arm. If it is judged to be too small this will only be presented descriptively.

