### **2.1.2.3 ANTIBIOTIC PRESCRIPTIONS**

There are three outcomes related to antibiotic prescriptions for pre-defined infections throughout the trial. Information regarding antibiotics will be obtained from the 12 months notes review, the SystmOne reports, and the post antibiotic telephone call. The outcomes of interest are:

- 1) Antibiotic usage in terms of number of prescriptions,
- 2) Number of days of treatment,
- 3) Defined daily dose (DDD),

Each outcome will be calculated separately for all antibiotics of interest, and split by antibiotic type (penicillin, and non-penicillin) as well as antibiotic class (see spreadsheet: K:\ID\ALABAMA\STATS\2. Stats Plan and Sample Size\SAP\ABX categories & DDD for analysis\_07Aug2023.xlsx). A list of the pre-defined infections of interest can be found in Appendix G of the protocol, and Appendix II of this document. Long term antibiotic prescriptions, defined as periods of continuous use for  $\geq 3$  months used for prophylaxis or “anti-inflammatory” indications will be excluded from the analyses.

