#### **2.1.2.3.2 NUMBER OF DAYS OF TREATMENT**

This outcome will be derived from the start and stop dates across the different data sources: the SystmOne report and the notes review (Variables *ABXPRESTARTDAT*, *ABXPRESTOPDAT*) and hospital prescribing report. The total number of days the participant was taking antibiotics for each prescription event will be added to give the total days prescribed antibiotic treatment for the 12-month period. This will be calculated as the stop date minus the start date plus one, if there is no evidence of antibiotic usage this outcome will be zero. If a patient has the antibiotic usage outcome (above) missing, then this outcome will also be missing.

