#### **2.1.2.4 HOSPITAL ADMISSIONS**

Information regarding hospital admissions will be obtained from the HES data, post antibiotic day 28-30 telephone call, and the notes review. This outcome will be derived as:

- i) A binary variable (yes/no) if there is any evidence that the participant had a hospital admission in the 56 days after the start of a primary event, during the 12 months post-randomisation,
- ii) The number of hospital admissions in the 56 days after the start of a primary event, during the 12 months post-randomisation. If there is no evidence of hospitalisation this outcome will be zero,
- iii) The total number of days of hospitalisation in the 56 days after the start of a primary event, during the 12 months post-randomisation. If there is no evidence of hospitalisation this outcome will be zero.

Outcomes above only apply to admissions in the 56 days after start of a primary event, an exploratory analysis will also be conducted for all admissions during the 12 months post-randomisation.

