## 2.3 SAMPLE SIZE

The primary outcome was initially treatment response failure defined as the percentage of re-prescription of an alternative antimicrobial within 28 days of an index prescription. A total sample size between 1592 and 2090 participants provided 80-90% power to detect a clinically important absolute difference of 7.9% in re-prescription rate at one year between groups (i.e. reducing from 19.8% in the control group to 11.9% in the PAAP group) at 5% level of significance (2-sided). The sample size had been adjusted assuming 50% of participants will require at least one prescription within 1 year from randomisation and allowing for 10% dropout. Participants are classed as enrolled at the point of randomisation.

The primary outcome was then changed to 'effects of PAAP on penicillin prescribing', defined as 'The proportion of participants who receive prescriptions for a penicillin attending for predefined conditions where a penicillin is the first-line recommended antibiotic (see Appendix II) during the course of routine primary care up to 12 months post randomisation. A total sample of 848 (i.e. 424 per group) was required to provide 90% power to detect an increase in the proportion of penicillin prescription from 4% (Usual Care) to 14% (PAAP) over the year after randomisation at 5% level of significance (2-sided) and 10% attrition. The sample size has been adjusted assuming 50% of participants will require at least one prescription within 1 year from randomisation. At 80% power, the sample size required was 656 (i.e. 328 per group). The table below also provides the sample size required if not all participants have reached 12 months follow-up.

Power	% Difference	Total sample size (all reached 12 months FU)	Total sample size (80% reached 12 months FU)	Total sample size (90% reached 12 months FU)
80%	10%	656	820	729
	15%	372	465	413
90%	10%	848	1060	942
	15%	472	590	524

Results from our recent analysis, using data extracted from the SystmOne database, suggested that there were an average of 110 patients per average practice size of 6000 who fulfilled our inclusion criteria.

- 1) Adults (over 18 years),
- 2) Penicillin allergy in electronic health records,
- 3) And in receipt of a penicillin, cephalosporin, tetracycline, quinolone, or macrolide class antimicrobial in the previous 24 months.

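### At the plan's own 4% v 14%, the median-regression fallback in SAP section 5.2 reports a difference of 0 for penicillin days and penicillin DDD

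*SAP*

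**What the plan says.** SAP section 5.2 fits a linear mixed model to days of antibiotic use, DDD, symptom duration and length of hospital stay, and reports an adjusted mean difference. If residual plots show violated assumptions, a transformation is tried. After that, "If there is still evidence that the assumptions have been violated a quantile regression will be implemented", with an adjusted median difference, 95% CI and P-value. The only way out of that model is non-convergence: "If the quantile regression does not converge an unadjusted quantile regression will be attempted", and a Mann-Whitney test follows if that fit fails too.

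Section 2.1.2.3 requires days and DDD to be "split by antibiotic type (penicillin, and non-penicillin) as well as antibiotic class". On non-users, section 2.1.2.3.2 says "if there is no evidence of antibiotic usage this outcome will be zero", and section 2.1.2.3.3 says the same for DDD. Section 2.1.2.4 treats length of stay likewise: "If there is no evidence of hospitalisation this outcome will be zero".

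Section 2.3 sizes the trial to "detect an increase in the proportion of penicillin prescription from 4% (Usual Care) to 14% (PAAP"), and adds: "The sample size has been adjusted assuming 50% of participants will require at least one prescription within 1 year from randomisation".

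Section 5.2 has one low-frequency exception, which allows descriptive reporting only: "Defined daily dose (DDD) split by class, is expected to be small for some classes in each randomised arm". It does not name days by class or the penicillin/non-penicillin split. Section 5.3 does provide for excess zeros in the count outcomes, through robust standard errors. Section 5.2 has no counterpart.

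**The concern.** A median stays at 0 until about half of the arm has a non-zero value. The plan expects far fewer than half of either arm to receive a penicillin, so a difference in medians cannot show the effect the trial is designed to produce. The trigger for leaving the median model is also the wrong one. It asks whether the model converges, not whether the median suits the data, and a fit that settles on 0 does converge.

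If the fallback is reached, two named secondary outcomes would be reported as a median difference of 0, which readers could take as no effect. The interval and P-value would not be usable, although section 4.4 reads any P-value below 0.05 as significant.

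**Working it through.** **Inputs from the SAP.** Penicillin use 4% v 14%; 50% with at least one prescription; 10% attrition; 848 randomised 1:1; non-users coded 0.

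**The plan's sample size.** For two proportions with d = 0.10 and mean proportion 0.09:

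- n' = [1.96 × √(2 × 0.09 × 0.91) + 1.2816 × √(0.04 × 0.96 + 0.14 × 0.86)]² / 0.10² ≈ 170.0, rounded up to 171.
- With continuity correction: n = (n'/4) × [1 + √(1 + 4/(n'd))]² ≈ 189.5, rounded up to 190.
- 2 × 190 / 0.5 / 0.9 = 844, or 846 in equal arms, against 848 stated. This reproduces the plan's figure. Without the correction the total is 760.

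The division by 0.5 implies that 4% v 14% applies to participants with a prescription. The outcome definition in section 2.1.1 instead counts all participants, so both readings are carried.

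**Zero shares.** Retained per arm: 848 × 0.9 / 2 ≈ 381 (381.6).

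| Reading | Users | Zeros | Zeros among 381 per arm |
|---|---|---|---|
| Rates apply to all | 4% v 14% | 96% v 86% | 366 v 328 |
| Rates apply to the 50% prescribed | 2% v 7% | 98% v 93% | 373 v 354 |

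With 381 participants, the binomial probability that the PAAP sample median exceeds 0 is about 7 × 10⁻⁶³ at 14% use, and about 6 × 10⁻²⁰ at double that rate.

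**Does adjustment change this?** Median regression was solved exactly on arm, age, prior prescriptions, QOF count and practice indicators. Assumptions not in the SAP:

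- courses drawn from 5, 7, 7, 7, 10 and 14 days;
- DDD equal to course length × 0.5, 1, 1, 1.5 or 2;
- log-odds of use 0.15 per SD of age, 0.15 per prior prescription and 0.1 per QOF disease, with practice SD 0.3;
- 20, 40 or 80 practices.

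Results for penicillin days and penicillin DDD:

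- Adjusted median difference 0 in 3,600 of 3,600 runs (300 runs × 12 settings).
- With covariate effects one, two or three times as strong (days only): 0 in 1,200 of 1,200.
- Bootstrap of individuals: 0 of 400 resamples non-zero at each rate pair, so the interval is 0 to 0.
- Separate runs with other course lengths and covariate effects also gave 0 every time, and the fit solved every time.

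In the same 3,600 runs the adjusted mean difference (ordinary least squares with practice-cluster-robust errors) was detected as follows:

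| Outcome | 2% v 7% | 4% v 14% |
|---|---|---|
| Days | 88–93% | 99–100% |
| DDD | 80–83% | 98–99% |

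**Is the fallback likely to be reached?** After log(1+y), residual skewness was still 4.2–4.4 (2% v 7%) and 2.6–2.8 (4% v 14%).

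**Is the P-value usable?** One iterative routine gave no convergence warning in 3,600 fits and coefficients below 0.000001. With no true effect it still gave P<0.05 in 55% (4.5% users) and 33% (9% users) of 200 data sets, from rounding alone. This is specific to that software.

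**Other outcomes.** Total users are 50%. Assuming nobody receives both types, non-penicillin users are 50% less 2% v 7% = 48% v 43%, or 50% less 4% v 14% = 46% v 36%. Share of 200 runs with a median difference of 0, as covariate effects strengthen:

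| Outcome | ×1 | ×2 | ×3 |
|---|---|---|---|
| Total days, 50% v 50% users | 82% | 38% | 16% |
| Non-penicillin days, 48% v 43% | 95% | 60% | 32% |
| Non-penicillin days, 46% v 36% | 100% | 90% | 62% |

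With equal use in both arms (40 practices, ×1), the difference was 0 in 100% of runs up to 40% users, 97% at 45%, 85% at 50% and 67% at 55%.

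**The case against.** The strongest case accepts the result for penicillin days and penicillin DDD and contests its breadth and weight.

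- **Breadth.** The SAP gives no rates for sparse classes or length of stay, and for total and non-penicillin days the median is often non-zero under stronger covariate effects. A half-zeros rule would bar median regression in some of those cases too. This stands in part: the cut-off is a judgement and not a sharp boundary. However, the rule acts on observed zeros, so it applies only where an arm's median sits at or next to 0.
- **Readings.** Reproducing 848 favours 2% v 7% of all randomised, so 46% v 36% non-penicillin users rests on the less likely reading. This is fair, but it leaves the penicillin result unchanged.
- **Existing cover.** Sections 2.2.1 and 2.3 list penicillin among antibiotic classes, so the descriptive-only clause might reach penicillin DDD. Section 2.1.2.3 lists type and class separately, and the clause does not reach penicillin days. Section 1.2 allows justified deviations, and histograms by arm are required, but neither repairs the stated rule.
- **A narrower repair.** A fit with zero medians could be added to the non-convergence trigger, which would open the Mann-Whitney test. That test did reject in 100% of simulated trials at 4% v 14% with 848 participants. It would work as a test, but would give up the adjusted estimate.
- **Evidence.** The false-positive rates come from one routine that the SAP does not name, and detection rates depend on assumed course lengths. The mean difference was checked by least squares with cluster-robust errors, not by the mixed model of section 5.2, and bootstrap intervals for the mean were not checked. These limits stand, but the zero result for penicillin does not depend on them.

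**Conclusion.** The concern holds: the fallback is wrong as written for penicillin days and penicillin DDD. On the plan's own figures, 86% to 98% of values in each arm are 0 and the adjusted median difference is 0 whether or not PAAP works. The fallback is conditional, but a spike of that size makes it likely to be reached, and the Mann-Whitney step would not open in fits that converge as these did. This conclusion needs only that use stays well below half in each arm.

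The same is likely for days in sparse antibiotic classes and for 56-day length of stay, but that is an assumption. For total and non-penicillin days and DDD, the median difference may be 0 or unstable, depending on the observed share of users.

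The consequence is limited to secondary outcomes. The primary relative risk (section 4.1) and the penicillin prescription rate ratio (section 5.3) still test the penicillin effect. The change should be made; confidence is medium.

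**What to change.** Add one rule to section 5.2, fixed before unblinding:

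- Median regression is not used for penicillin days, penicillin DDD, or any other days, DDD or length-of-stay outcome in which about half or more of the values in either arm are zero.
- For these outcomes, keep the adjusted mean difference that section 5.2 names first, with practice-cluster-robust or bootstrap confidence intervals, in line with the robust errors in section 5.3.
- Extend the descriptive-only exception from DDD by class to days by class, and to any outcome with too few users or admissions.
- A two-part model is optional and supportive only.

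The cost is a sentence or two of wording and little programming. There are two downsides. A few long courses or stays can influence a mean difference, and cluster-robust intervals can be slightly too narrow. With no effect (2,000 runs per setting), type I error was 4.6–6.1% for days and 4.5–5.4% for DDD at 2.5–15% users, 4.3–6.3% at 41–50% users, and 3.6–5.3% for length of stay at an assumed 2–30% admitted. The highest value, 6.3%, came with 20 practices.

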## 2.4 RANDOMISATION AND BLINDING IN THE ANALYSIS STAGE

During their call with the research team, participants were asked if they had taken any antibiotics in the previous two weeks; if they had, the randomisation/baseline call was postponed until the participant was free of antibiotic use for two weeks. The research team arranged another call to take place when the participant had been free of antibiotic use for two weeks. During the call, the participants were asked to complete the baseline assessment and the member of the research team performed randomisation. Randomisation was performed using Sortition (PC-CTU's in-house online randomisation system) according to the current version of the SOP PC-CTU\_SOP\_IT104. Allocation was minimised by general practice, age, number of antibiotic prescriptions up to 24 months prior to randomisation, and number of Quality Outcome Framework registered diseases, to ensure balance of allocation of these baseline covariates. Patients were randomised to either usual care (with subsequent monitoring for antibiotic prescriptions and follow-up for trial outcomes as determined by the clinical indication for antibiotics) or the PAAP intervention arm using an allocation ratio of 1:1. Both the participants and the recruiter knew which arm they were randomised into. The trial statistician will remain blinded to treatment allocation when performing the final analysis. Unblinding of the allocation will take place in accordance with SOP PC-CTU\_SOP\_ST105.

N.B. Patients randomised to the PAAP trial arm, who do not attend an appointment for PAT, will continue to be followed up unless consent is withdrawn.

**NOTE:** There have been some errors made during the randomisation procedure, at least one participant's minimisation data has been entered incorrectly onto Sortition (and cannot be corrected). As such, the information collected on the baseline CRF (data from OpenClinica) will be used as covariates in the analysis regardless of the information that was used for the randomisation. Information from both the baseline CRF and the information used in the randomisation (Sortition) will be presented in the baseline table.

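### SAP 5.2: if the adjusted quantile regression does not converge, the fallback drops all four minimisation factors at once, when dropping GP practice alone may be enough

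*SAP*

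**What the plan says.** Section 5.2 covers symptom duration, days of antibiotic use, DDD and length of hospital stay. The first choice is a linear mixed model with GP practice as a random effect. If diagnostics fail, a transformation is tried. Then: "If there is still evidence that the assumptions have been violated a quantile regression will be implemented".

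The quantile regression has no random effect. It adjusts for randomised group, age, prior antibiotic prescriptions, "number of QOF registered diseases, and GP practice as covariates". Two more steps follow: "If the quantile regression does not converge an unadjusted quantile regression will be attempted" and "if the model still does not converge a non-parametric approach such as a Mann-Whitney U test will be adopted". No step between the fully adjusted and the unadjusted model is given.

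Section 2.4 on randomisation says: "Allocation was minimised by general practice, age, number of antibiotic prescriptions up to 24 months prior to randomisation", and names the QOF disease count as the fourth factor.

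**The concern.** The covariates lost at the unadjusted step are exactly the minimisation factors. If those factors predict the outcome, an analysis that ignores them has standard errors that are too wide for the balance the allocation created, so it loses precision and tends to be conservative.

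It also departs from the rest of the SAP. Sections 4.1, 5.1, 5.2 and 5.3 adjust every first-choice model for all four factors. Section 3.4 says the primary and secondary models account for site. For the related count outcomes, section 5.3 falls back on robust standard errors and then other count models, and does not tell the analyst to drop covariates.

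Of the four terms, age, prior count and QOF count are three simple covariates. Practice adds roughly one coefficient per practice, so it is the natural term to remove first. Finally, Mann-Whitney gives no adjusted effect estimate, and the wording that introduces it only as an example leaves the last test open.

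**Working it through.** **1. The plan's own figure.** The SAP gives no SD, R² or power for the continuous outcomes. Its only relevant figures are in section 2.3, for the primary outcome. For 4% v 14%, 90% power, two-sided 5% and a continuity correction, I get 190 per arm. Then 190 / 0.5 / 0.9 = 422.2, rounded up to 423 per arm, total 846 against the stated 848. This reproduces. Taking off 10% attrition, 848 × 0.9 = 763, rounded to 764 for equal arms, is the analysed number used below.

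**2. Share of zeros.** Sections 2.1.2.3.2, 2.1.2.3.3 and 2.1.2.4 set days, DDD and hospital days to zero when there is no event. Section 2.3 assumes 50% of participants need a prescription within a year, so about half of the antibiotic days and DDD values would be zero. The penicillin split has more: if 4% and 14% of all participants receive a penicillin, 96% and 86% are zero. Symptom duration is scored only after a prescription event (2.1.2.2), so this does not carry over to it.

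**3. Loss by formula.** Let R² be the share of outcome variance explained by the covariates (assumed), and let the adjusted test have 80% power.
- Simple random allocation: unadjusted power = Φ[(1.96 + 0.8416)·√(1 − R²) − 1.96].
- Allocation fully balanced on the covariates: unadjusted power = Φ[(1.96 + 0.8416) − 1.96/√(1 − R²)], and the true size is 2Φ[−1.96/√(1 − R²)].

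| R² | Power, random | Power, balanced | Size, balanced |
|---|---|---|---|
| 0.05 | 78.0% | 78.5% | 4.4% |
| 0.10 | 75.7% | 76.9% | 3.9% |
| 0.20 | 70.7% | 72.9% | 2.8% |
| 0.30 | 65.0% | 67.7% | 1.9% |

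**4. Simulation on zero-heavy days of treatment.** N = 764, 300 replicates per scenario, an assumed effect, and adjustment for prior count and age. QOF count, practice and minimisation were not simulated. The Monte Carlo standard error is up to about 3 points.

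| Zeros | Covariate | Adjusted median regression | Unadjusted median regression | Mann-Whitney | Adjusted rank analysis |
|---|---|---|---|---|---|
| 30% | weak | 0.72 | 0.54 | 0.84 | 0.85 |
| 30% | strong | 0.84 | 0.40 | 0.78 | 0.85 |
| 50% | weak | 0.29 | 0.48 | 0.78 | 0.78 |
| 50% | strong | 0.01 | 0.52 | 0.64 | 0.73 |
| 60% | weak | 0.00 | 0.00 | 0.65 | 0.67 |
| 60% | strong | 0.00 | 0.00 | 0.57 | 0.69 |

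Mann-Whitney against the adjusted rank analysis loses about 0 to 12 points. Mann-Whitney against adjusted median regression gains power in five of the six rows. In the sixth (30% zeros, strong covariate) the adjusted median regression rejected in 10% of null replicates, so its 0.84 is flattered.

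At 50% zeros with no effect, unadjusted median regression with default standard errors rejected in about 59% of replicates, so its entries of 0.48 and 0.52 are not interpretable as power. At 60% zeros both medians were 0 in every replicate.

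**5. Other assumptions.** A second simulation compared Mann-Whitney with a covariate-adjusted proportional-odds model and gave 78% v 81%, 74% v 79% and 65% v 74% at correlations of 0.17, 0.33 and 0.44. Its adjusted test rejected about 7% under the null, within error for 300 runs. A further check gave losses of 0 to 7 points, mostly within simulation error, and null rejection of about 23 to 47% for unadjusted median regression.

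**6. Cause of non-convergence.** Assuming 40 practices (the SAP gives no number), 60 replicates and one software routine, the full quantile model failed in 3 to 8% of runs and the model without practice in 0 to 2%.

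**The case against.** The strongest reply is that this path is remote: the linear model must fail, then the transformation, then convergence. It concerns secondary outcomes only, and the expected effect of ignoring minimisation factors is conservative. Section 3.4 also pools sites with fewer than 5 participants, which limits sparse practice levels, and section 1.2 requires deviations to be justified. The wording of the last step would already allow a covariate-adjusted rank test. All of this stands, and it keeps the point minor. It does not remove it: the stated rule still discards three simple covariates with no reason given.

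Four stronger readings are tempting, and the SAP does not support them:
- **The fallback costs power against the analysis it replaces.** At the SAP's 50% prescription share the simulation shows the reverse for Mann-Whitney, because a median difference is nearly uninformative there.
- **The prior prescription count is in effect the baseline value of the outcome.** The covariate counts prescriptions over up to 24 months (12 for pilot participants). The outcomes are days and DDD over 12 months, for predefined infections, without long-term prophylaxis. A high correlation cannot be assumed.
- **GP practice is the known cause of non-convergence.** It is plausible, and the small check points that way, but nothing in the SAP establishes it.
- **All four outcomes are zero-heavy.** This is not shown for symptom duration.

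**Conclusion.** The point holds as a minor one. Section 5.2 removes all four minimisation factors in one step when removing the many-level practice term alone may be enough. The primary analysis is unaffected, and the secondary analyses are affected only if the fallback is reached.

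The loss against a covariate-adjusted rank or ordinal analysis is about 0 to 12 power points. That range rests wholly on assumed covariate strength, effect size and zero share. The size to expect in this trial cannot be derived from the SAP.

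The unadjusted quantile step is poor for a separate reason. With about half the values at zero, the median difference is near-degenerate, and default standard errors gave unreliable p-values. Restoring covariates alone would not cure that, so the repair also needs a model suited to many ties at zero.

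**What to change.** Replace the last two steps of section 5.2:

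1. If the quantile regression with GP practice does not converge, drop GP practice only. Keep randomised group, age, prior antibiotic count and QOF count, and use practice-clustered bootstrap standard errors.
2. If that fails, or if about half or more of the values are zero (likely for antibiotic days, DDD and length of stay), fit a proportional-odds model with the same covariates and practice-clustered standard errors in place of the unadjusted quantile regression and Mann-Whitney. Report the odds ratio with its 95% CI.

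Mann-Whitney is essentially the unadjusted form of that model, so the second step keeps the same kind of comparison and adds the covariates.

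Cost: a few sentences of SAP text, no new data and a little more computing. Downsides: a proportional-odds assumption, and an effect measure that differs from the mean or median differences reported for other outcomes.
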